6.3 Assessments During Study

The following data will provide the basis for assessing protocol compliance and safety as well as between-group differences in several efficacy variables. Data for each of the variables will be recorded on the days shown in the Time-Events schedule (Appendix E) or until death, discharge from the intensive care unit, or unassisted ventilation for 48 hours.

Reference Measurements

The following parameters will be measured and recorded between 4:00 and 10:00 A.M. using the values closest to 8:00 A.M. on the days specified in the Time-Events schedule (Appendix E). The following conditions will be ensured prior to measurements: no endobronchial suctioning

for 10 minutes; no invasive procedures or ventilator changes for 30 minutes. All vascular pressures will be zero-referenced to the mid-axillary line.

- 1. If receiving positive pressure ventilation:
 - (a) Ventilator mode
 - (b) PEEP level
 - (c) Total minute ventilation
 - (d) Tidal Volume
 - (e) Plateau airway pressures
- 2. FiO₂
- 3. PaO₂, PaCO₂, pH, and SpO₂
- 4. Hemodynamic values
 - (a) Systemic arterial systolic, diastolic and mean blood pressures
 - (b) Heart Rate (beats/min)

Values for the following variables will be recorded for the dates shown in the Time-Events Schedule (Appendix E). If the measurements are not obtained during the 6-hour reference interval (4:00 to 10:00 A.M.), then the value obtained closest in time to the reference interval on the respective date will be recorded. If more than one value is obtained during the reference interval, then the value obtained closest to 8:00 A.M. will be recorded.

- 5. Blood hemoglobin concentration, white blood cell count, prothrombin time (PT), and platelet count.
- 6. Serum electrolytes, creatinine, and glucose
- 7. Units of insulin at time of daily glucose value (infusion) or total insulin in the 6 hours prior to the glucose value (subcutaneous)
- 8. Serum total protein, albumin, magnesium, phosphorus
- 9. Requirements for the following medications (Y / N):
 - (a) Sedatives and narcotics
 - (b) Neuromuscular blocking agents
 - (c) Vasopressors
 - (d) Pro-kinetic agents (e.g. metoclopramide, erythromycin, lactulose, or sorbitol)
 - (e) Laxatives and fiber products
 - (f) Anti-diarrheal agents
 - (g) Methylprednisolone equivalents greater than 20 mg
- 10. Frontal Chest Radiograph Lung Injury Score
- 11. Brussels Score data (Bernard, 1997)
 - (a) Worst PaO₂ / FiO₂ ratio for the date.
 - (b) Worst systolic blood pressure for that date
 - (c) Worst creatinine, bilirubin, and platelet count for the date
 - (d) Use of vasopressors
 - (e) Glasgow Coma Score

- 12. Blood for cytokines, mediators, and markers of inflammation. Plasma obtained from two, 10 ml EDTA anti-coagulated blood samples will be divided immediately after centrifugation into 4 equal 2 ml aliquots in specified tubes and frozen at -70^oC. Blood will be collected on days 0, 3, 6, and 12.
- 13. Urine for isoprostane metabolites. Urine obtained from the patients will be collected in an 8 ml sample tubes and divided into 4 aliquots of 2 ml each in specified tubes and frozen at -70°C. Urine will be collected on days 0, 3 and 6
- 14. Enteral feeding volume and number of calories received for the previous 24 hours.
- 15. Number and type of gastrointestinal intolerances for the previous 24 hours.
- 16. Episodes of VAP
- 17. Episodes of bacteremia
- 18. Episodes of Clostridium dificile-induced diarrhea

Samples will be sent to a central repository to be stored (as described below). Samples will be identified by random number during shipment and storage in the central repository. In the future, when approved studies are received at the CCC the CCC will instruct the repository to prepare the appropriate samples for shipment. The key relating the ARDSNet study number to the new specimen number will be kept at the CCC in a locked file. The CCC does not record or store unique patient identifiers (such as initials, date of birth, hospital record numbers, addresses, phone numbers, etc.) in the database. All data released by the CCC for studies will be linked to the specimen but will be de-identified. The link (key) between the de-identified database and the patient will be removed two years after the primary publication.

Note: Urine and plasma collected for this trial will be frozen and stored at a Bio repository for future research.

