• **Titles:** Prospective, Randomized, Multi-center Trial of Initial Trophic Enteral Feeding Followed by Advancement to Full-calorie Enteral Feeding vs. Early Advancement to Full-calorie Enteral Feeding in Patients with Acute Lung Injury (ALI) or Acute Respiratory Distress Syndrome (ARDS)

• Objectives:

 To assess the safety and efficacy of initial trophic enteral feeding followed by advancement to full-calorie enteral feeding vs. initial advancement to full-calorie enteral feeding management strategies in reducing mortality and morbidity in patients with ALI or ARDS

• Hypotheses:

- 1. Initial trophic feeding followed by full-calorie enteral feeding will improve clinical outcomes (specifically increase the number of ventilator-free days to day 28 and decrease the 60-day, hospital mortality) in patients with ALI or ARDS by reducing systemic inflammation and the number of feeding complications as compared to early, full-calorie enteral feeding.
- **Study Design:** Multi-center, prospective, randomized, controlled clinical trials.
 - 1. A maximum of 1000 patients will be enrolled.
 - 2. Patients randomized to trophic enteral feeds will receive trophic feeding rates (20 kcal / hr) for 144 hours prior to being advanced to full-calorie feeding rates which will continue for the duration of mechanical ventilation up to study day 28.
 - 3. Patients randomized to full-calorie enteral feeds will be advanced to full-calorie feeding rates on initiation of feeding and will continue to receive full-calorie feeds for the duration of mechanical ventilation up to study day 28.
 - 4. Patients will be followed to the earlier of 60 days or hospital discharge. In addition, vital status will be ascertained at 90 days.

• Sample Size/Interim Monitoring:

This study compares the use of initial trophic enteral feeds followed by advancement to full-calorie enteral feeds versus initial full-calorie feeds in patients with ALI or ARDS. The trial will accrue a maximum of 1000 patients providing about 500 patients treated initially with trophic enteral feeds to be compared against about 500 patients treated initially with full-calorie enteral feeds. This provides 90 % power to detect an absolute difference of 2.25 ventilator-free days assuming a mean of 14 and standard deviation of 10.5 ventilator-free days (data from FACTT study) using a two sided p = 0.05 significance level.

- 2 The principal analysis will be intent-to-treat, based upon randomization assignment.

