3.2 Secondary Endpoints

1. The secondary efficacy variable for the trial is mortality prior to hospital discharge with unassisted breathing. Patients alive in hospital at day 60 will be considered to have survived.

- 2. Mortality before hospital discharge home, with unassisted breathing, to day 90. Patients alive in hospital to day 90 will considered to have survived
- 3. Number of ICU-free days at 28 days after randomization
- 4. Number of organ failure-free days at 28 days after randomization. Organ failure will be defined by previously validated definitions for renal, circulation, central nervous system, hematologic, and hepatic organ and system failures (Bernard, 1997).

Organ failure is defined as present on any date when the most abnormal vital signs or clinically available lab value meets the definition of clinically significant organ failure according to the Brussels Organ Failure Table. Patients will be followed for development of organ failures to death, hospital discharge or study day 28, whichever comes first. Each day a patient is alive and free of a given clinically significant organ failure will be scored as a failure-free day. Any day that a patient is alive and free of all 5 organ failures will represent days alive and free of all organ failure. Central nervous system dysfunction is evaluated using the Glasgow Coma Scale.

- 5. Number of days between the day of first meeting criteria for weaning-readiness (see Appendix G, section G.2.) and day 28 after randomization.
- 6. Mortality and VFDs in patients with pre-randomization $PaO_2/F_1O_2 \le 200$.
- 7. Change in plasma levels of IL-6, IL-8, VWF, SPD, and total protein concentrations from baseline to study day 3.
- 8. Ventilator free days and mortality prior to hospital discharge with unassisted breathing to day 60 and number of ventilator-free days to day 28 in patients with shock (defined in 2.1.2) at the time of randomization.

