- b. Guillain-Barré Syndrome
- c. Myasthenia gravis
- d. Upper spinal cord injury at level C5 or above
- e. Kyphoscoliosis or chest wall deformity resulting in severe exercise restriction (unable to climb stairs or perform household duties), secondary polycythemia, or respirator dependence

5. Severe Chronic Respiratory Disease

[figure not shown]
Any of the following is considered severe chronic respiratory disease and excludes a patient from being eligible for enrollment:

- 1. FEV₁ less than 20 ml/kg PBW (e.g. 1.4 L for a 70 kg person), or
- 2. FEV₁/VC less than 50% predicted, or
- 3. Chronic hypercapnia (PaCO₂ greater than 45 mmHg) and/or chronic hypoxemia (PaO₂ less than 55 mmHg) on $F_1O_2 = 0.21$, or
- 4. Radiographic x-ray evidence of any chronic over-inflation or chronic interstitial infiltration, or
- 5. Hospitalization within the past six months for respiratory failure in patients with chronic respiratory disease. (PaCO₂ greater than 50 mmHg or PaO₂ less than 55 mmHg or O₂-Sat < 88% on FiO₂ = .21).
- 6. Chronic restrictive, obstructive, neuromuscular, chest wall or pulmonary vascular disease resulting in severe exercise restriction, e.g., unable to climb stairs or perform household duties, secondary polycythemia, severe pulmonary hypertension (mean PAP greater than 40 mmHg), or respirator dependency.

C Trophic Feeding Protocol

D Full-calorie Feeding Protocol

Time-Events Schedule \mathbf{E}

Measurement/Event	Day 0	1	2	3	4	5	6	7	8	9	10	11	12	14	21	28	60
Demographics, History & Physical, Height, Weight	X																
Etiology of ARDS, site of sepsis if septic etiology	Х																
APACHE III Score ^C	Х																
HCG (in females)	Х																
Vital Signs (HR, SBP, DBP, Temp °C) *	Х	Х	Х	Х	Х	Х	Х	Х	Х	Х	Х						
Central Venous Pressure *	Α	Α	Α	Α	Α	Α	Α	Α	Α	Α	Α						
Fluids (In and Out) *	Х	Х	Х	Х	Х	Х	Х	Х									
Brussels Score ^B ~	Х	Х	Х	Х	Х	Х	Х	Х	Х	Х	Х	Х	Х	Х	Х	Х	
Glasgow Coma Scale	Х							Х								X**	
Ventilator Parameters (including FiO ₂) *#	Х	Х	Х	Х	Х		Х						Х		Х	Х	
Arterial Blood Gases (PaO ₂ , PaCO ₂ , pH) and SpO ₂	Х	Α	Α	Α	Α		Α						Α		Α	Α	
Serum Glucose, Na+, K+, HCO3-, Hgb	Х	Α	Α	Α	Α	Α	Α	Α	Α	Α	Α	Α	Α				
Creatinine, Platelets, Bilirubin, BUN Hct,	Х																
Chest X-ray (# quadrants for lung injury score)	Α	Α	Α	Α	Α	Α	Α	Α	Α	Α	Α						
Record Sedatives, narcotics, pressors * (Y/N)	Х	Х	Х	Х	Х	Х	Х	Х	Х	Х	Х	Х	Х				

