Serum magnesium and phosphorus	Х	Х	Α	Х	Α	Α	Α	Α	Х	Α	Α	Α	Α				
Total Protein and Albumin	Х	Х	Α	Α	Α	Α	Α	Х	Α	Α	Α	Α	Х				
Ventilator–Associated Pneumonia assessment ^v	Α	Α	Α	Α	Α	Α	Α	Α	Α	Α	Α	Α	Α	Α	Α	Α	
Insulin dose at time of glucose level	Α	Α	Α	Α	Α	Α	Α	Α	Α	Α	Α	Α	Α				
Location of Feeding tube (e.g., gastric, post-pyloric) *	Х	Α	Α	Α	Α	Α	Α	Α	Α	Α	Α	Α	Α				
Volume of tube feeds / Calories delivered *		Х	Х	Х	Х	Х	Х	Х	Х	Х	Х	Х	Х				
Number and type of Gastrointestinal Intolerances		Х	Х	Х	Х	Х	Х	Х	Х	Х	Х	Х	Х				
Pro-kinetic agents, anti-diarrheals, anti-emetics * (Y/N)	Х	Х	Х	Х	Х	Х	Х	Х	Х	Х	Х	Х	Х				
Prothrombin Time	Α	Α	Α	Α	Α	Α	Α	Α	Α	Α	Α	Α	Α				
Plasma for Cytokines IL-6 and IL-8	Х			Х			Х						Х				
Urine isoprostane metabolites	Х			Х			Х										
Whole blood for DNA	Х																
Episode of bacteremia (record positive blood cultures) *		Α	Α	Α	Α	Α	Α	Α	Α	Α	Α	Α	Α	Α			
Clostridium dificile diarrhea tests		Α	Α	Α	Α	Α	Α	Α	Α	Α	Α	Α	Α	Α			
Vital Status §																Х	Х

A=When available

 $^{^{\}text{C}}=$ Labs not available in the 24 hours before randomization must be obtained

V = VAP assessment from available CXR, sputum culture, gram stain and WBC until extubated or day 28, whichever occurs first *= Data gathered at times indicated or until 48 hours UAB, whichever occurs first **=On day 28 or hospital discharge dates.

B=Records clinically available creatinine, platelets, bilirubin, SBP and vasopressor use

^{~=}Data gathered on days 0-28 or until d/c from study hospital

^{#=}Measure during reference period (0600-1000); other values may be obtained closest to 0800 on the specified calendar date §=Measure at 90 days and 12 months as part of Long Term outcome.

F Adverse Events

1. Procedures for Reporting Adverse Events

Assuring patient safety is an essential component of this protocol. Each participating investigator has primary responsibility for the safety of the individual participants under his or her care. The Principal Investigator will evaluate all adverse events. The Study Coordinator must view patient records for possible adverse events throughout the study period. All adverse events occurring within the study period must be reported in the participants' case report forms.

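### Section 6.3 stops recording Brussels organ-failure data at ICU discharge or 48 hours of unassisted ventilation, while section 3.2 and Appendix E require them to hospital discharge or day 28

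*Protocol*

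**What the plan says.** Three places in the protocol set the end of organ-failure data collection.

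- **Section 3.2, item 4** defines organ-failure-free days at 28 days: "Patients will be followed for development of organ failures to death, hospital discharge or study day 28, whichever comes first". The scoring rule is: "Each day a patient is alive and free of a given clinically significant organ failure will be scored as a failure-free day".
- **Section 6.3** introduces its list by saying that each variable is recorded on the days in Appendix E "or until death, discharge from the intensive care unit, or unassisted ventilation for 48 hours". Item 11 of the list is headed "Brussels Score data (Bernard, 1997)" and covers worst PaO2/FiO2, systolic pressure, creatinine, bilirubin, platelets, vasopressor use and Glasgow Coma Score. No item is excepted from the stop.
- **Appendix E** marks the Brussels row with footnotes B and ~. Footnote ~ reads: "Data gathered on days 0-28 or until d/c from study hospital". A separate footnote, *, reads: "Data gathered at times indicated or until 48 hours UAB, whichever occurs first". It is attached to rows such as vital signs, fluids, ventilator parameters and feeding volume, but not to the Brussels row.

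**The concern.** Section 6.3 is the data-collection section, and it says that its data support between-group comparisons of efficacy variables. Read literally, it ends Brussels recording earlier than the endpoint definition requires. For a patient who is off the ventilator for 48 hours, or out of the ICU, but still in hospital, a later renal, hepatic, haematologic, circulatory or neurological failure would not be entered.

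The loss need not be equal in the two arms. Under 6.3 the stop is set largely by when the patient weans. Weaning time also drives ventilator-free days, and section 2.3 hypothesises that initial trophic feeding increases them. If one arm weans sooner, its patients leave observation sooner. Organ failure is named in the primary objective (2.1), and organ-failure-free days are a listed secondary efficacy variable analysed in the same way as the primary endpoint (section 7). A difference in ascertainment would therefore enter that treatment comparison directly. An analysis plan cannot recover values that sites stopped recording.

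**Working it through.** **Comparing the texts.** The protocol gives no figure for this point, so there is none to reproduce.

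| Source | Applies to | Recording ends at the first of |
|---|---|---|
| 3.2, item 4 | organ failures | death, hospital discharge, day 28 |
| Appendix E, footnote ~ | Brussels row | day 28, discharge from study hospital |
| 6.3, lead-in | all listed variables, including item 11 | death, ICU discharge, 48 hours of unassisted ventilation |
| Appendix E, footnote * | other rows, not Brussels | the scheduled days, 48 hours of unassisted breathing |

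The first two rows agree and are specific to organ failure. The third covers the same data with an earlier stop. The fourth shows that the schedule keeps two stopping rules apart and gives the longer one to Brussels data. Section 6.3 merges them.

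**What is in dispute.** Only the days from the 6.3 stop to hospital discharge (or death or day 28, if sooner) differ between the versions. Days after hospital discharge are unobserved under all of them.

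**A ceiling on that window.** Inputs:

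- The Study Summary sizes the trial "assuming a mean of 14 and standard deviation of 10.5 ventilator-free days".
- 48 hours is 2 days.
- The share of patients with any ventilator-free days, p, is not stated. I take p = 1 as one extreme, p = 0.78 as an assumption based on the 22% 28-day hospital mortality in Table 3, and p = 0.70 as a further assumption.

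Mean days from 48 hours of unassisted breathing to day 28 ≈ mean VFD − 2 × p:

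- p = 1.00: 14 − 2.00 = 12.0 days; 12.0/28 = 43%
- p = 0.78: 14 − 1.56 = 12.44 days; 12.44/28 = 44%
- p = 0.70: 14 − 1.40 = 12.6 days; 12.6/28 = 45%

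The formula slightly understates the mean when some patients have fewer than 2 ventilator-free days. Gamma models of ventilation duration matched to the planning figures do not take it above 12.8 days (12.8/28 = 46%). The range is therefore about 12 to 12.8 days.

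**Why this is not an estimate of lost data.** The interval runs to day 28, whereas the disputed window ends at hospital discharge. The protocol gives no length of stay to subtract. The figure also covers the 48-hour rule alone and treats weaning as final. ICU discharge before 48 hours, a return to the ventilator, or death after weaning would change it somewhat, and the document does not allow those to be quantified either.

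**The case against.** The strongest reply is that the documents largely settle the matter themselves. Section 6.3 sends the reader to Appendix E for timing. Appendix E sets the stop row by row, withholds the 48-hour footnote from the Brussels row and gives it the hospital-discharge footnote, in agreement with 3.2. Two specific, agreeing provisions stand against one general lead-in sentence covering 18 items, with a loosely worded conjunction. Many sites would follow the schedule.

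This stands as a reason to expect limited harm. It does not remove the conflict: 6.3 states a different stop for the same data and exempts nothing.

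Three stronger readings are tempting, and the protocol does not support them.

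- **Some 45% of the organ-failure window is lost.** That share includes days after hospital discharge, which no version observes.
- **A 2.25-day difference in ventilator-free days produces a calculable false gain or loss in organ-failure-free days.** This would need an organ-failure rate among the unrecorded days, which the protocol does not give. It would also need the whole benefit to come from faster weaning. Section 3.1 describes VFDs as a composite of mortality and ventilation time. A benefit through fewer deaths would affect observed days differently, so even the sign is open.
- **The protocol is deficient because it does not say how days after discharge or transfer are scored.** That detail is commonly left to the analysis plan, which is not at hand. Aligning 6.3 would not settle it in any case.

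**Conclusion.** The inconsistency is real and is in the current text. It concerns collection of data for one secondary endpoint. The primary endpoint, the sample size and the error control are untouched.

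If 6.3 is followed, in-hospital organ failures after the earlier stop go unrecorded, and the timing of that stop depends on weaning. Ascertainment could then differ between arms if weaning times differ. That is a possible bias of unknown size and direction, conditional on sites following 6.3 rather than Appendix E. The only number available is the ceiling of about 12 to 12.8 days per patient, which rests on the planning mean of 14 VFD and on assumed values for the share of patients with any ventilator-free days. The text should be corrected because the remedy is cheap and data missed during the trial may not be recoverable at analysis.

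**What to change.** In section 6.3, add one sentence exempting item 11 (Brussels data) from the ICU-discharge and 48-hour stop, so that it is collected to death, hospital discharge or day 28, whichever comes first, as 3.2 item 4 and Appendix E already state.

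The cost is small. Sites that had followed 6.3 would enter clinically available creatinine, platelets, bilirubin, systolic pressure and vasopressor use for ward days that Appendix E already schedules; footnote B lists exactly these items. No treatment or clinical procedure changes.

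One detail needs care in the drafting. Item 11 also lists Glasgow Coma Score and PaO2/FiO2, which footnote B does not, and Appendix E gives the Glasgow Coma Scale its own row, marked only on days 0, 7 and 28 or hospital discharge. The new sentence should say whether the exemption covers those two items, so that it does not create a second mismatch with the schedule.

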6.4. Assessments after Hospitalization

As explained in the Background and Significance section of this proposal, it is very important to obtain long term outcomes data on the patients enrolled in the Nutrition trial as it may have a significant effect on long term morbidity, and it would be very unfortunate to carry out a large trial of this kind and have no mechanism to determine longer term outcomes.

The following data, as well as vital status, will be collected at 6 and 12 months after ICU discharge. We will collect this data through telephone interviews with patients. In addition, we will verify duration of survival for patients lost to follow-up or noted to have died using the Centers for Disease Control and Prevention's National Death Index (National Death Index, 2000). We will use each patient's social security number (SSN) for an exact NDI match. We will collect contact information for the patient and alternative contact information on up to 3 individuals. This information and the SSN will be collected on paper at the time of consent, and forward via secure fax to the CCC. Contact information and SSN will be maintained on paper and will not appear in the CCC database.

The following instruments will be used in data collection. This battery of instruments will be pilot tested to guarantee feasibility. The text explains the alternative tests available pending the results of the pilot testing.

1. Health-related Quality of Life:

- a. SF-36 (consider the SF-12 if the length is too long in pilot testing). *Estimated* administration time: 6 minutes.
- b. Euro-QOL (EQ-5d): Estimated administration time 2 minutes.
- c. Functional Assessment of Chronic Illness Therapy (FACIT; 13 questions) (if length is too long in pilot testing, this instrument will be deleted due to over-lap with SF-36); *Estimate administration time: 3 minutes*

2. Psychological Outcomes:

- a. Depression and Anxiety: Hospital Anxiety and Depression Scale (14 questions) *Estimated administration time: 5 minutes*
- b. Post-Traumatic Stress Disorder (PTSD): Impact of Events Scale—Revised (22 questions); *Estimated administration time: 3 minutes*.

3. Neurocognitive Outcomes:

Telephone version of the Mini-Mental State Examination (TMMSE) (16 items); *Estimated administration time: 5 minutes*

4. Physical Activity Outcomes:

- a. Overall: Functional Performance Inventory-Short Form (32 questions) (alternative: deleting this instrument (due to overlap with the Physical Function Domain of SF-36) or use the Katz ADL (6 questions) & the Lawton IADL, (8 questions), if length is too long in pilot testing) *Estimated administration time: 5 minutes*
- b. Work disability: Return to Work Custom-made Questionnaire (12 questions—will reduce number of questions if length is too long in pilot testing); *Estimated administration time:* 2 *minutes*.
- 5. Health care utilization: Custom-made instrument developed based on University of Toronto ARDS Outcome Study instrument provided by [name] (27 questions), will reduce number of questions if this instrument is too lengthy in pilot testing; *Estimate administration time:* 8 *minutes*

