4.1 Number/Source/Screening

The trial will accrue a maximum of 1000 patients over a 3-4 year interval. Approximately 500 patient will be randomized to initial trophic feeding and 500 to initial full calorie feeding. The first 272 patients were enrolled in a 2 x 2 factorial design with an Omega 3 Fatty acid rich medical food versus a control isocaloric medical food. This portion of the trial was stopped by the DSMB for futility.

Patients with ALI or ARDS will be recruited from intensive care units at NIH ARDS Network centers. Study coordinators will visit intensive care units daily to identify potential candidates for enrollment (see inclusion criteria, section 4.2, and exclusion criteria, section 4.3. Permission to approach patients and/or their families will be requested from the attending physicians. All patients meeting the inclusion criteria will be entered on a screening log. If the patient is not enrolled, the screening log will include information explaining why enrollment did not occur (exclusion criteria, attending physician denial, patient refusal, etc. see Appendix L).

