Mortality will be compared at interim data analyses using Kaplan Meier estimates at 60 days and their associated standard errors. This analysis will be stratified as above and a test for interaction of treatment with strata will be presented. At the end of the study sixty-day mortality will be compared using a Mantel-Haenzel test as long as all patients can be followed. If not the method used for the interim analyses will be used.

Other Endpoints

The number of ICU-free days, Organ-Failure Free days, and days from first weaning readiness will be analyzed in the same manner as is described above for the primary endpoint. In addition we will test for interactions between treatment and gender and race as per NIH guidelines (National Institutes of Health, 2001).

Changes in plasma levels of IL-6, IL-8, and protein will be compared in two analyses. An analysis of covariance will test for a treatment effect on the day 3 value of these variables using the day 0 value as a covariate. In addition, a multivariate analysis of variance will test for a baseline difference between day 3 and day 0.

Table 3 illustrates the detectable differences for endpoints, assuming 1000 patients enrolled, 90% power, and a two-sided alpha-level of 0.05.

Table 3: Detectable Differences for Secondary Endpoints

Variable	Incidence or Mean	Standard Deviation	Detectable Difference
PaO ₂ / FiO ₂	155	73	15
ICU free days	13.4 days	12.6 days	2.6 days
Shock free days	19.1 days	4.93 days	2.23 days
Plasma IL-6 (pg/ml)	1252	862	177
Plasma IL-8 (pg/ml)	149	93	19
28 day hospital mortality	22%		8.2%
90 day hospital mortality	25.4%		8.6%

Changes in physiologic lung indices on days 1-7 will be compared using a multivariate analysis of variance.

Twice during the early part of the study, the DSMB will evaluate the glucose control between the trophic and full-calorie arms to ensure that the levels of blood glucose are not clinically different between the groups over the first 6 days of the study. These evaluations will occur after approximately 100 and 250 patients are enrolled in the study. Should the blood glucose values differ between the groups at these evaluations, the guidelines for controlling blood glucose levels for the remainder of the study may be adjusted in an attempt to equalize the blood glucose levels for the study.

8 Data Collection and Site Monitoring

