Health care utilization	University of Toronto ARDS Outcome study instrument (4)	-Developed and used in large longitudinal cohort of ALI survivors (4)	27 items; 8 minutes; Continuous

^{*} Also will be determined from a National Death Index via participant's Social Security Number.

Administration of phone surveys will be centralized at 2 sites: Johns Hopkins and LDS Hospital, where the 2 Principal Investigators are affiliated. Being in different time zones, this 2-site approach will allow flexibility in accessing patients across the US while also concentrating our oversight activities. Manuals of Operations will be used for training, reference and quality assurance review.

NOTES:

- (1) Estimated time for completion. This was based on pilot testing, published estimates and the experience of the ARDS Network investigators. The full telephone interview will be piloted prior to implementation.
- (2) Return to Work assessment. There are no pre-existing comprehensive survey instruments for measuring return to work and work disability in patients with lung disease. We derived our custom-made instrument from an approach used by one member of the Long-term Outcomes Committee ([name] and colleagues) to measure work disability in asthma and COPD.

K.2 Statistical Considerations for Long Term Outcomes

A number of dichotomous and continuous measures of long-term efficacy of the treatment will be analyzed.

Dichotomous measures:

- 1) Survival times will be compared for the treatment arms using log rank test.
- 2) Proportions of patients alive without major disabilities will be compared between the treatment arms using Cochran-Mantel-Haenszel test. Major disability is defined for surviving patients that are prevented from working due to a respiratory condition.
- 3) Proportions of patients alive without disability in activities of daily living (ADL) or instrumental activities of daily living (IADL) will be compared across treatment arms using Cochran-Mantel-Haenzsel test. Major disability ADL and IADL are defined based on functional performance inventory for a patient who has at least one activity in the "body care" and "maintaining household" subscales, respectively, that s/he cannot perform at all due to health reasons or does it with much difficulty.

Each of the comparisons will be done based on the data collected at 6 months, and 1-year follow up times.

Continuous measures:

- 1) Primary measure of disability defined by functional performance inventory.

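### Section 6.4 times the 6- and 12-month interviews and vital status from ICU discharge, which feeding may shift, and Appendix E gives a different vital-status schedule

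*Protocol*

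**What the plan says.** Section 6.4 fixes the origin of long-term follow-up: "The following data, as well as vital status, will be collected at 6 and 12 months after ICU discharge". The mode is telephone: "We will collect this data through telephone interviews with patients". For deaths there is a second source, the National Death Index: "we will verify duration of survival for patients lost to follow-up or noted to have died using the Centers for Disease Control".

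The Appendix E vital-status row sits on a grid of study days, with marks at days 28 and 60. Its footnote § adds: "Measure at 90 days and 12 months as part of Long Term outcome". It gives no 6-month point and does not mention ICU discharge.

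K.2, on the dichotomous long-term measures, says: "Each of the comparisons will be done based on the data collected at 6 months, and 1-year follow up times". It states no origin there, nor for the log-rank comparison of survival times.

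ICU stay is itself an outcome. Secondary endpoint 3 in section 3.2 is "Number of ICU-free days at 28 days after randomization", counted from randomisation.

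**The concern.** A comparison at 6 or 12 months is cleanest when both arms are measured at the same time since randomisation. An origin that occurs after randomisation, and that treatment may move, carries any effect on ICU stay into the long-term comparison: the arm that leaves the ICU later is interviewed later and is exposed to death for longer before its nominal 6- or 12-month status.

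Two further problems follow. A patient who dies in the ICU never reaches ICU discharge plus 6 months, so section 6.4 taken literally assigns no vital-status date. And sections 6.4 and Appendix E give different long-term vital-status schedules, so staff cannot tell which 12-month date applies. The interview date is fixed at data collection. A later analysis plan could choose an origin for survival, but it could not re-time interviews already held.

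**Working it through.** **1. The passages side by side**

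| Place | Times | Origin |
|---|---|---|
| Study summary | vital status at 90 days | not stated |
| Section 6.4 | interviews and vital status at 6 and 12 months | ICU discharge |
| Section 6.6 | vital status at 28, 60 and 90 days, until discharge home on unassisted breathing | not stated |
| Appendix E, footnote § | vital status at 90 days and 12 months | study-day grid |
| K.2 | comparisons at 6 months and 1 year | not stated |

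Section 6.4 and footnote § disagree on whether there is a 6-month vital-status point, and their 12-month dates differ by each patient's time to ICU discharge. Nothing else in the protocol re-anchors the interviews to randomisation.

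**2. Reproducing the figure used for scale**

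Inputs: SD of ICU-free days 12.6 and detectable difference 2.6 days (section 7, Table 3), "assuming 1000 patients enrolled, 90% power, and a two-sided alpha-level of 0.05"; allocation from section 4.1: "Approximately 500 patient will be randomized to initial trophic feeding and 500 to initial full calorie feeding".

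- Detectable difference = (1.960 + 1.282) × 12.6 × √(2/500) = 2.58 days, which rounds to the stated 2.6.
- Power at 2.6 days with 500 per arm = 0.904, against the stated 0.90.

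The Table 3 row reproduces.

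**3. Size of a between-arm timing shift**

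Shift as a share of follow-up (6 months = 182.6 days, 12 months = 365.25 days). Only the 2.6-day row comes from the protocol; 1 and 10 days are an assumed range.

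| Shift | Share of 6 months | Share of 12 months |
|---|---|---|
| 1 day | 0.5% | 0.3% |
| 2.6 days | 1.4% | 0.7% |
| 10 days | 5.5% | 2.7% |

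**4. What that shift could do to a result** (all rates assumed)

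- Continuous score improving by 0.1 to 1.0 SD per 6 months: bias = rate × shift / 182.6. For 2.6 days this is 0.001 to 0.014 SD; for 10 days, 0.005 to 0.055 SD.
- For comparison, with 50% to 75% of each arm interviewed, the effect detectable at 90% power is 3.24 × √(2/(500 × 0.50)) = 0.29 SD down to 3.24 × √(2/(500 × 0.75)) = 0.24 SD.
- Proportion dead, at 0.25% to 1% of patients dying per month: change = rate × 2.6 / 30.4 = 0.02 to 0.09 percentage points.

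**5. Spread between patients**

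With an assumed ICU stay of 2 to 60 days, a 6-month interview (183 days) falls 183 + 2 = 185 to 183 + 60 = 243 days after randomisation. If the spread is similar in both arms, it adds noise and no bias.

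**6. Where ICU deaths are recorded**

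The fixed-day checks (28, 60 and 90 days), the date and cause of death in the Appendix K battery, and the National Death Index all capture them. K.2 compares survival times and proportions alive without disability. An ICU death can enter the first through its date and counts as a failure in the second, with no interview date needed.

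**The case against.** The strongest reply is that little depends on this. A timing difference between arms arises only if feeding changes ICU stay among survivors, and at the protocol's own detectable difference it is a few days in 6 or 12 months. Interviews are for survivors, so a dead patient needs no call date. Long-term outcomes are not among the section 3 endpoints. K.2 already plans a survivor average causal effect analysis for the larger problem of who survives and can be contacted. An unstated survival origin is detail that an analysis plan commonly supplies. Anchoring interviews to recovery is also a defensible choice.

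Most of this stands, and it rules out three stronger readings that a reader might infer:

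- **That the long-term comparison is materially biased.** The documents show no such effect, and the sizes above are far below what the interviews could detect.
- **That ICU deaths go missing or drop out of the log-rank test.** They are captured by several routes, and K.2 does not say that survival runs from ICU discharge.
- **That the clock starts about 15 days after randomisation on average**, from 28 − 13.4 = 14.6. The protocol gives no scoring rule for ICU-free days. If deaths score zero (an assumption), Table 3's 22% 28-day mortality puts the survivor mean at 13.4/0.78 = 17.2, and the origin nearer 28 − 17.2 = 10.8 days.

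The reply does not remove the conflict between section 6.4 and footnote §. The causal-effect analysis does not address timing, and the interview schedule cannot be repaired at the analysis stage.

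**Conclusion.** The point holds as a badly chosen and inconsistently stated time origin. Section 6.4 uses a post-randomisation event that treatment may shift, Appendix E gives another vital-status schedule, and K.2 does not settle the matter. If feeding changes ICU stay, the arms are assessed at slightly different times since randomisation: about 2.6 days at the Table 3 detectable difference. That figure is only a rough guide, because ICU-free days may mix deaths with length of stay. Under the assumed recovery rates the resulting bias is at most 0.014 SD at 2.6 days. The missing vital-status date for ICU deaths is a gap in section 6.4's wording, not a loss of deaths. The primary endpoint is untouched. The change is worth making because it is cheap and removes a dependence on treatment that serves no stated purpose.

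**What to change.** - **Section 6.4:** set the interviews and vital status at 6 and 12 months after randomisation, with a stated interview window.
- **K.2:** state that survival times and the 6- and 12-month status run from randomisation.
- **Appendix E, footnote §:** list 6 and 12 months, keeping the 90-day point.

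With this change the planned difference in assessment time between arms is zero, and every patient, including one who dies in the ICU, has a defined 6- and 12-month date. The cost is wording and call scheduling, with no added visits and no change to any power or sample-size figure. The downside is that a few patients may still be in hospital at 6 months; the interview window should say how they are handled.
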